Evaluation of the Efficacy of Exparel Delivered Into the Hip Capsule During Hemiarthroplasty

NCT03502018

06/19/2017

Study Purpose and Rationale

Hip fractures are a growing concern in orthopaedic trauma as the baby boomer generation ages. As of 2012, it is estimated that at least 250,000 people age 65 and older are hospitalized for hip fractures (1). While the initial injuries involve a great deal of pain and discomfort, the controlled trauma of undergoing reparative surgery adds to patients' strain. Exparel (liposomal bupivacaine), is a local analgesic that has become part of the multifaceted approach to control postoperative pain. However, studies evaluating this drug's utility in assisting with postoperative pain control have focused primarily on use with total joint arthroplasty (2,3,4). Exparel is a form of Bupivacaine that is encapsulated in microscopic, spherical, lipid-based particles. Its microscopic structure resembles a honeycomb composed of numerous chambers separated by lipid membranes (5). Upon injection, these particles release Bupivacaine over an extended period of time via erosion and reorganization of the lipid membranes. This mode of analgesia delivery has become more widely-studied in recent years in a variety of surgical settings.

Phase IV economic trials for adults undergoing open colectomy and ileostomy reversal demonstrated that using liposomal bupivacaine in multimodal analgesia regimen was associated with decreased opioid use, shorter lengths of stay, and decreased hospitalization costs compared to more traditional, opioid-based pain control (6,7). Another study involving patients undergoing implant-based breast reconstruction found statistically significant decreases in length of stay (1.5 versus 2.0 days) and VAS pain scores at 4,8,12,16, and 24 hours postoperatively in patients treated with liposomal bupivacaine (8). Orthopedic studies have also been performed on arthroplasty patients to compare periarticular injections of Exparel to other pain control drugs and delivery modalities. One study from the Journal of Arthroplasty compared Exparel compared to femoral nerve blocks. While the data was inconclusive as to whether there was a significant difference in terms of postoperative pain control there were compelling findings indicating that Exparel patients had improved ambulation on the day of surgery, increased distance ambulated throughout their hospital stays, and shorter lengths of stay. The authors also argued that using periarticular Exparel injections blocks can potentially decrease the need for secondary invasive procedures, decrease preoperative time, avoid delays in surgery, and decrease the risk of associated quadriceps weakness compared to femoral nerve blocks. (3) Another large study compared 686 primary total hip arthroplasty (THA) patients receiving standard pain management protocol to 586 patients receiving the standard protocol augmented by intraoperative liposomal bupivacaine. In the bupivacaine group, there was a significant decrease in total narcotic use (specifically during postoperative day 2), a greater degree of achievement with regard to physical therapy milestones, and decreased average length of stay (9).

There are few randomized studies on trauma patients. This research protocol was adapted from the Orthopedic Trauma Association in a recently (now suspended) call for research proposals for trauma patients to increase or knowledge or the best way to treat post-surgical pain for traumatic intracapsular hip fractures undergoing hemi arthroplasty through a posterior approach

Research Design and Methods:

Exparel is a long-acting and sustained release formulation of the local anesthetic, bupivacaine HCl. Recent studies have supported its efficacy following total joint arthroplasty, but little is known about Exparel's effectiveness in hip fracture patients. This investigation will study the effects of Exparel on postoperative pain following hip fracture surgery. This is a single center, randomized prospective double blinded study of 50 patients with hip fractures that will have intracapsular hip hemiarthroplasties and are 65 years or older. Twenty-five patients will be treated with intraoperative injections of Exparel. Current standard of care does not include any injection of pain medication during hip hemiarthroplasty. There is no 'standard treatment', but to use multimodal IV and oral analgesia. The control group consisting of the remaining 25 patients will receive 'standard treatment' (which is multimodal IV and oral analgesia). Therefore, saline is the appropriate placebo and control injection for this study. There are minimal to no risks associated with the injection of saline into the soft tissues about the hip and will take <2 minutes to complete. This follows the same methodology used by the

department of anesthesiology at Maimonides Medical Center during their previous Exparel Knee study. The surgeries will be performed by five surgeons who will inject use their standard treatment or in the interventional group participants will relieve 20 cc of Exparel diluted with 40 ml 0.25% bupivacaine into the surrounding hip capsule: external rotators, gluteus medius, gluteus minimus, gluteus maximus, tensor fascia lata, vastus lateralis, and subcutaneous tissues.

Both the patient and the researcher following the patient postoperatively will be blinded. While the treating surgeon will be able to notice the difference between the placebo and Exparel, the outcomes outlined below will be recorded by the blinded Orthopaedic Research Resident who has no clinical responsibilities during his/her year of research and does not participate in operative procedures

Description of Outcome Measures

There are two overall aims of this investigation. The first aim is to identify whether Exparel has an impact on postoperative pain and function following open treatment of hip fractures. The hypothesis is that injecting Exparel into the hip capsule and surrounding tissues will decrease narcotic use, and in turn decrease the risk of associated side effects including medically induced delirium, constipation, and decreased alertness. The second aim of the study is focused on examining whether increased pain control leads to better postoperative outcomes? When pain is better controlled via non-narcotic measures, overall patient comfort will improve while sparing cognitive function, decreasing time to ambulation, and accelerating progress with physical therapy. Quicker recovery times will then produce shorter hospital stays, which would yield better overall patient satisfaction and overall improved outcomes. Patients with intracapsular hip fractures will undergo hip hemiarthroplasty using a bipolar prosthesis placed via a posterior approach. Primary outcome measures include postoperative visual analogue scale (VAS from 0-10) pain scores at 12, 24, 36, 48 hours after surgery, time to ambulation with physical therapy, need for postoperative total morphine equivalent, and delirium scale measurements. Secondary outcomes measures will compare length of stay, discharge disposition (home or skilled nursing facility), 30-day readmission rates, and adverse events leading to ICU care or reoperation. All patients in both groups will have access to breakthrough pain medication which will either be Percocet for moderate to severe pain (pain scale of 4-10, acetaminophen or Toradol for mild to moderate pain (pain scale of 2-4).

Study Procedures

There will be a total of 50 patients enrolled in this randomized blinded prospective two arm study. The participants will be randomized into either the control or the EXPAREL treatment group, with 25 patients in each cohort with the use of the randomization program available at randomizer.org. The injection of Exparel or a placebo will not change the surgical procedure being performed, the implants used, operative time, or rehab protocols and therefore do not alter the standard of care by participating in this study. The research design was formulated by the Orthopaedic Trauma Association in a recently-suspended call for research proposals; for the purposes of this study we will be performing a modified version of their requested protocol (please refer to the attached PDF).

Study Population

Inclusion criteria:

The inclusion criteria include men and women sixty-five years of age and older with isolated intracapsular hip fractures undergoing hemi arthroplasty through a posterior approach with the ability to consent to the study.

Exclusion criteria

Patients will be excluded if they have an extracapsular hip fracture, suffer from any form of cognitive compromise that leaves them unable to consent, or if they are treated with any surgical modality other than hip hemiarthroplasty.

Study Drugs or Devices:

The only drug that will be used in this Exparel. Exparel is FDA approved for local infiltration in to wound for postoperative pain relief. No IND number will be required.

Study Instruments (e.g., Questionnaires, Interview Outlines, Focus Group Guides

Does the delivery of Exparel into hip capsule during hemiarthroplasty will affect the following primary outcome measures?

1. Decreased pain on a postoperative visual analogue scale (VAS) pain scores at 12, 24, 36, 48 hours after surgery
2. There will be a decreased time to ambulation with physical therapy
3. There will be a decreased need for postoperative total morphine equivalent

Does the delivery of Exparel into hip capsule during hemiarthroplasty affect any of the following secondary outcome measures:

1. Decrease. Delirium scale measurements.
2. Decreased length of stay

We will also look record:

1. Discharge disposition (home or skilled nursing facility)

The following primary outcomes will be recorded for each patient post-op day 1: -Delirium Scale (CAM)- Total morphine equiv. post-surgery (Oral Percocet will be converted into morphine equivalents and pain score will be recorded at the time of administrating narcotics.

VAS pain scores combined with and 11 point numerical rating scale (NRS) for subjective pain at 4, 8, 12, 24, and 48, hours after surgery.

Time to ambulate with physical therapy.

The following secondary outcomes will also be recorded for each patient from post-op day until discharge/readmission:

- Length of stay
- discharge disposition (home vs. skilled nursing vs. inpatient rehab)

The orthopaedic surgery team routinely grades pain postoperatively and uses a standardized pain scale to address patient's pain. The pain scales and primary outcomes will be recorded by the blinded orthopaedic research resident who does not participate in surgical procedures or have clinical responsibilities, but is familiar with and has previously utilized all of these systems.

[name], anesthesiologist at Maimonides Medical center, performed a similar study at our center using Exparel vs. a saline control injected into the posterior knee capsule in patients undergoing total knee arthroplasty. Therefore, collaboration with the Anesthesia Department, which has already completed a similar study, allows us to adopt their methodology for this study. Both the patient and the researcher following the patient postoperatively will be blinded. While the treating surgeon will be able to notice the difference between the placebo and Exparel, the outcomes outlined above will be recorded by the blinded Orthopaedic Research Resident who has no clinical responsibilities during his/her year of research and does not participate in operative procedures.

Study Protocol

Subjects will be divided into two groups, A and B. Group A (saline control) will receive 20 ml of saline mixed with 40cc 0.25% bupivacaine while group B (study) will receive 20 cc of Exparel mixed 40cc 0.25% bupivacaine. Multimodal analgesia will be used to supplement pain control. Each patient will receive 1g Tylenol (not to exceed 4g in 24 hours). All subjects will have access to rescue analgesics. Oxycodone 5mg q4 PRN for moderate pain (4-<7, and Morphine 2mg q4 PRN for severe breakthrough pain (Pain score of 7 or greater).

The technique was modified from the protocol of [name]: Once implants are in place and confirmed to be appropriately placed by full arc range of motion, wound will be copiously irrigated, and final hemostasis is obtained. The control group involved injection of 40 cc of 0.25% bupivacaine HCl (Marcaine) with 20 cc of normal saline injected in a systematic fashion with self-retaining retractors exposing the surgical field. Multiple 20cc syringes with 22 gauge spinal needles are used. Starting medially and posteriorly, the capsule is injected circumferentially in 10-12 locations with 2-3cc in each location, watching for the capsule to swell slightly. The posterior capsule is injected around the neck of the implant. Care is taken to ensure that the needle only penetrates the capsule 1-2 cm to prevent sciatic nerve or femoral nerve injury. Any remaining solution is then used to inject the abductors, and tensor fascia lata. If any is remaining, the subcutaneous layer is injected. Post operative notes and charting will state "patient is a study patient and either Exparel or saline was administered" to preserve blinding.

After 25 patients are enrolled, the study will be paused and an update provided to the IRB.

Statistical Analysis

Descriptive summary statistics (means, standard deviations, ranges, etc.) for each of the endpoints will be produced for all subjects. The dose of all opioids administered will be converted into morphine equivalents for analysis. Since this is a two-sided analysis with continuous variables, the T-test will be performed on pain scores and morphine equivalents comparing Exparel to saline where an α of 0.05% will be considered significant. The duration of post analgesia observed with EXPAREL will be compared with saline controls receiving. Additionally, the incidence of postsurgical AEs will be summarized for all subjects.

Power analysis

We performed 2 power analysis.

Presuming that pain scores are normally distributed, and equal standard deviations, 1:1 ratio of people in each group, alpha=.05, Power=.80 the sample size per group will vary by the projected mean difference between groups and the standard deviation. The table below give you a few different calculations for a simple T-Test difference between two independent groups.

Keep in mind that these estimates are only for a simple t-test. As you look to do multivariate analyses you will need much more to allow for additional analyses and incomplete or problem data.

Mean Difference	standard deviation	Sample size per grp
1	1	17
1.5	1	8
1	2	65
1.5	2	29

For the 25 patients in each group you mentioned, a mean difference of 2, with a standard deviation of 1.5, you would have a power of .99.

Using data from another study with Exparel:

Assuming a difference of at least 3 points on an eleven point pain scale from 0 to 10 nrs pain scale and a standard deviation = 2.2 the effect size is expected to be at least .90 and sample of 25 in each group (Exparel versus control) should provide > 90% Power to detect a significant difference with alpha = 0.05.

Either way we should have enough power to successfully complete the study without a beta error.

Descriptive summary statistics (means, standard deviations, ranges, etc.) for each of the endpoints will be produced for all subjects receiving EXPAREL. The dose of all opioids administered will be converted into morphine equivalents for analysis. Duration of analgesia observed with EXPAREL will be compared with controls not receiving Exparel.

Number of Subjects

There will be a total of 50 patients enrolled in this randomized blinded prospective two arm study. The participants will be randomized into either the control or the EXPAREL treatment group, with 25 patients in each cohort.

Recruitment

Both men and women sixty-five years of age and older with isolated intracapsular hip fractures undergoing hemi arthroplasty through a posterior approach with the ability to consent to the study. Patients will be offered to participate in the study when they are ready for consent for surgery.

Informed Consent Process

Any patient that meets inclusion criteria, without any exclusion criteria will be offered to participate in the study. Either a resident on the project or PI or CoPI (Only staff members with CITI training will obtain informed consent) will consent the patient in a private area which will be signed by either the PI or Co-PI. Patient will be explained the risk and benefits that are listed in the consent form. We will not guarantee any benefit from the use of Exparel.

Economic Burden to Subjects

Patients will have to pay for that standard of care (ER visit, hospital care and payment for the surgical procedure), and will not be billed for any experimental part of the project.

Compensation

There will be no compensation for participation in the study.

Compensation for Research-Related Injury

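### The design rationale justifies a saline placebo, but the control injection that is specified contains 100 mg of bupivacaine, so the trial's contrast is not settled

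*Combined protocol and SAP*

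**What the plan says.** Research Design and Methods reasons in steps. It states: "Current standard of care does not include any injection of pain medication during hip hemiarthroplasty". It says of the comparator arm: "The control group consisting of the remaining 25 patients will receive 'standard treatment' (which is multimodal IV and oral analgesia". From this it concludes: "Therefore, saline is the appropriate placebo and control injection for this study". The risk statement that follows covers saline only: "There are minimal to no risks associated with the injection of saline into the soft tissues about the hip". Plain bupivacaine is mentioned in that section only for the experimental arm, which is to receive "20 cc of Exparel diluted with 40 ml 0.25% bupivacaine into the surrounding hip capsule". The section gives no volume or mixture for the control injection, and its sentence on what the surgeons inject cannot be parsed: "five surgeons who will inject use their standard treatment or in the interventional group".

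Study Procedures describes the two injections in the same terms: "The injection of Exparel or a placebo will not change the surgical procedure being performed".

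Study Protocol does give a control mixture: "Group A (saline control) will receive 20 ml of saline mixed with 40cc 0.25% bupivacaine". The injection technique later in that section repeats it, with the same volumes of bupivacaine and saline. The experimental arm there is 20 cc of Exparel with the same 40 cc of bupivacaine.

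Statistical Analysis describes the t-test on pain scores and morphine equivalents as Exparel against saline, and the comparison of analgesic duration as being with saline controls.

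**The concern.** The control injection defines the question that the trial answers. The rationale leads a reader to expect an inactive control, added to ordinary systemic analgesia. The specified control is an active local anaesthetic infiltration, which the rationale says standard care does not include. An argument from the absence of injected analgesia to saline does not justify that mixture, and a risk statement about saline does not cover it.

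Two things are at stake. If the specified mixture is given, the result is the increment of Exparel over bupivacaine infiltration. With the rationale left in place and the comparator called saline, a null result could be reported as no better than placebo, and a positive one as better than standard care. The design would support neither statement. If instead a control without bupivacaine is given, as the rationale implies, Exparel and plain bupivacaine vary together between the arms and their effects cannot be separated.

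**Working it through.** The plan gives no figure for the anaesthetic content of the control injection, so there is none to reproduce. The check is the composition of each arm under each description.

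**Inputs**
- Control, Study Protocol (group description and injection technique): 40 ml of 0.25% bupivacaine + 20 ml saline.
- Experimental arm, Research Design and Methods and Study Protocol: 20 ml Exparel + 40 ml of 0.25% bupivacaine.
- Control, Research Design and Methods: saline, mixture not stated. Zero plain bupivacaine is inferred from the rationale.
- Conversion: 0.25% = 2.5 mg/ml.

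**Content of the specified control injection**
- Plain bupivacaine: 40 ml × 2.5 mg/ml = 100 mg.
- Total volume: 40 + 20 = 60 ml.
- Concentration: 100 / 60 = 1.67 mg/ml.
- Share of the volume that is bupivacaine solution: 40 / 60 = 66.7%.

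**Plain bupivacaine by arm**

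| Description of control | Exparel arm | Control arm | Difference | What the comparison estimates |
|---|---|---|---|---|
| Study Protocol | 100 mg | 100 mg | 100 − 100 = 0 mg | Exparel added to bupivacaine infiltration versus that infiltration alone |
| Implied by Research Design and Methods | 100 mg | 0 mg (inferred) | 100 − 0 = 100 mg | Exparel plus bupivacaine versus saline |

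**Does any other text decide between them?**
- The statement under Study Drugs or Devices that Exparel is the sole drug does not help. The Exparel arm contains plain bupivacaine wherever its mixture is given, so that statement cannot be literal under either description.
- The appeal to the centre's earlier knee study does not help. That study is described only as Exparel against a saline control.
- The analysis wording does not help. It names the groups without giving their content.

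**Power.** The stated power of .99 (25 per group, difference 2, standard deviation 1.5) reproduces at 0.996 by the two-sided t-test and 0.997 by the normal approximation. The point here concerns what is compared, not the sample size.

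**The case against.** The best defence is that saline is shorthand. Each arm is named by the 20 ml component that differs, within a common bupivacaine mixture. Study Protocol uses the label that way when it calls the bupivacaine mixture a saline control. Research Design and Methods also speaks of Exparel injections before giving the Exparel–bupivacaine mixture, and the blinding note for the chart names only Exparel or saline. On this reading the t-test wording is a correct group label, and calling the control a placebo is normal in an add-on design. In addition, only the Study Protocol section states a control mixture. It does so twice and consistently, so there is one specification with an ill-fitting rationale, not two rival specifications. If it is followed, the randomisation, test and estimate are unchanged, and the harm lies in how the result is later described.

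Much of this stands. The labels in Statistical Analysis and Study Procedures are not errors in themselves. The 100 mg difference between arms is an inference, and that branch arises only if staff depart from the specified mixture. The shorthand reading does not rescue the rationale, however. Its premise is that standard care contains no injected analgesic, its conclusion is drawn from that premise, and its risk sentence covers saline alone. None of these fits an injection with 100 mg of bupivacaine, and no passage resolves the conflict.

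**Conclusion.** The concern holds and should be corrected before the trial is conducted or reported under this text. The rationale for the control and the control as specified contradict each other. The difference is 100 mg of plain bupivacaine, two-thirds of the volume of the specified control injection. The arms differ by 0 mg of plain bupivacaine under the Study Protocol mixture and by 100 mg under the control that the rationale implies. Only the first contrast isolates Exparel, and it does so against bupivacaine infiltration, not against placebo or standard care without an injection.

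The conclusion rests on reading the rationale as implying a bupivacaine-free control, since Research Design and Methods states no control mixture. The mismatch between the specified injection and the premise and risk sentence does not depend on that inference. No error of power or sample size is claimed.

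**What to change.** Reconcile Research Design and Methods with Study Protocol so that one control injection, with its full composition, is stated in both. Which injection that should be is for the sponsor and is not decided here. Then:

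- Make the standard-care rationale and the risk sentence in Research Design and Methods fit that control, and rewrite the unreadable sentence on what the surgeons inject.
- In Statistical Analysis, name the contrast in the t-test and duration sentences, and carry it into any conclusion. If both arms receive plain bupivacaine, it is Exparel added to bupivacaine versus bupivacaine alone. If the control does not contain it, it is Exparel plus bupivacaine versus saline, with an explicit statement that an effect cannot be attributed to Exparel alone.
- Use the word placebo in Research Design and Methods and in Study Procedures only in the sense that fits the stated control.

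The cost is a wording amendment to a few sentences in those four sections. Naming the contrast does not by itself change the sample size, the randomisation or the test.

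### Three conflicting primary-outcome lists with no lead outcome or multiplicity control, and a printed significance level of 0.05% that contradicts the 0.05 used for sizing

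*Combined protocol and SAP*

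**What the plan says.** The document gives three current lists of primary outcomes.

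- **Description of Outcome Measures:** "Primary outcome measures include postoperative visual analogue scale (VAS from 0-10) pain scores at 12, 24, 36, 48 hours after surgery, time to ambulation", followed by "need for postoperative total morphine equivalent, and delirium scale measurements".
- **Study Instruments, numbered list:** the pain item is "Decreased pain on a postoperative visual analogue scale (VAS) pain scores at 12, 24, 36, 48 hours after surgery". Time to ambulation and total morphine equivalents are items 2 and 3. Delirium now heads the secondary list: "Decrease. Delirium scale measurements".
- **Study Instruments, recording list that follows:** "The following primary outcomes will be recorded for each patient post-op day 1: -Delirium Scale (CAM" opens a list that also contains morphine equivalents, time to ambulation and VAS/NRS scores "for subjective pain at 4, 8, 12, 24, and 48, hours after surgery".

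The hypothesis in Description of Outcome Measures concerns opioids: "injecting Exparel into the hip capsule and surrounding tissues will decrease narcotic use". Both calculations under Power analysis are for pain scores.

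Statistical Analysis names a two-sided t-test for pain scores and morphine equivalents and prints the significance threshold as 0.05%. It does not say how the pain times are combined, and it names no test for time to ambulation or delirium. Both power calculations use alpha 0.05. Data and Safety Monitoring says that the pause after 25 patients will help show whether Exparel patients benefit, but not whether the arms will be compared.

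**The concern.** A confirmatory trial needs one statement, fixed before unblinding, of what result would make it positive. Here the set of primary outcomes depends on which section is read, and no section says whether one significant outcome is enough, whether all are needed, or which comes first. One significant pain time, or one significant outcome among several, could be reported as a positive primary result, and a reader could not tell it from chance.

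The threshold adds a second ambiguity that works in the opposite direction. Taken literally, 0.05% makes false positives rare but leaves the trial well short of the power for which it was sized.

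**Working it through.** **1. Counting the comparisons** (VAS combined with NRS taken as one score per time)

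| List | Pain times (h) | Ambulation | Morphine equivalents | Delirium | Total |
|---|---|---|---|---|---|
| Description of Outcome Measures | 12, 24, 36, 48 | primary | primary | primary | 4+1+1+1 = 7 |
| Study Instruments, numbered | 12, 24, 36, 48 | primary | primary | secondary | 4+1+1 = 6 |
| Study Instruments, recording | 4, 8, 12, 24, 48 | primary | primary | primary | 5+1+1+1 = 8 |

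**2. The plan's own sample sizes, and which alpha they fit**

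Inputs from Power analysis: 80% power, 1:1 allocation, two-sided t-test. The normal approximation is n per group = 2 (z₁₋α/₂ + z₀.₈₀)² (SD/difference)². For difference 1 and SD 1:

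- α = 0.05: 2 (1.960 + 0.842)² = 15.7, so 16; the exact t-test gives 17.
- α = 0.0005: 2 (3.481 + 0.842)² = 37.4, so 38; the exact t-test gives 41.

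| Difference / SD | Plan prints | t-test, α 0.05 | t-test, α 0.0005 |
|---|---|---|---|
| 1 / 1 | 17 | 17 | 41 |
| 1.5 / 1 | 8 | 9 | 20 |
| 1 / 2 | 65 | 64 | 153 |
| 1.5 / 2 | 29 | 29 | 70 |

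The plan's table reproduces to within one patient at 0.05 and not at all at 0.0005. With 25 per group, difference 2 and SD 1.5, power is 99.6% at 0.05 (the plan prints .99) and 82.5% at 0.0005. At the plan's effect size of .90 it falls from 88% to 31%.

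**3. Chance of at least one false-positive primary result**

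Condition: each comparison is tested at two-sided 0.05 and any one significant result counts as success. If the comparisons were independent, the chance is 1 − 0.95^k: 22.6% for k = 5, 26.5% for 6, 30.2% for 7 and 33.7% for 8. They are not independent, so null trials were simulated: 25 per arm, multivariate normal, t-tests. The correlations are assumptions, because the documents give none: 0.5-0.7 between pain times and 0-0.5 across outcomes.

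| Set tested | Chance of at least one false positive |
|---|---|
| Five with a named t-test (four VAS times, morphine equivalents) | 16-20% |
| Six (numbered list) | 19-24% |
| Seven (Description of Outcome Measures) | 21-28% |
| Eight (recording list) | 23-30% |
| Three (pain as a single item) | 12.5-14% |

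The rows for three, six, seven and eight assume a t-test on time to ambulation; those for seven and eight also treat delirium as continuous. Sensitivity checks:

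- Delirium as yes/no with Fisher's exact test, assumed incidence 10-30%: the seven give 19-26%.
- Pain-time correlation 0.8: the five give 15-16% and the seven 20-24%.
- Threshold of 0.0005 taken literally, independent tests: 1 − 0.9995^k is only 0.3-0.4% for six to eight tests. The cost is then the lost power in step 2.

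**4. Power if four pain scores are averaged**

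The SD of the mean is SD × √((1+3ρ)/4), a factor of 0.79 at ρ = 0.5 and 0.88 at ρ = 0.7. For a constant 1.5/2 effect (0.75 SD at one time), the mean has an effect of 0.75/0.79 = 0.95 or 0.75/0.88 = 0.85 SD.

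| 25 per group, 1.5/2 | Power at 0.05 | Power at 0.0167 (Holm's first step, three outcomes) |
|---|---|---|
| One early time | 74% | – |
| Mean, constant effect | 91% (ρ 0.5), 84% (ρ 0.7) | 80%, 70% |
| Mean, effect waning to 100, 100, 50, 0% (average 62.5%) | 54%, 45% | – |

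**The case against.** The strongest reply is that the plan leans towards pain even though it never says so formally. Research Design and Methods and Potential Benefits both describe the study's purpose in terms of pain, and both power calculations use pain. That stands as a reason to choose pain as the single primary outcome. It does not supply the missing declaration, a time point or a summary, and the stated hypothesis is about narcotic use.

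Second, 0.05% is probably a typing error for 0.05 or 5%. The recomputation supports that reading, and alone it would be a trivial correction. It is still the only decision threshold in the analysis section, so it must be right.

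Third, the counts of seven, six and eight are a reading. The numbered list has three items, and the recording list might be for data collection only, although it calls its contents primary. If VAS and NRS were separate scales, that list would hold 13 comparisons rather than 8. The larger error rates also add tests that the plan does not name. These points are fair, and the answer is the range shown: the most lenient reading still gives more than twice the nominal 5%. Counting only named t-tests in the recording list makes six comparisons and 18-22%.

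Fourth, there are loose ends that the lists alone do not settle: the window for morphine equivalents (day 1 or total), VAS against NRS, pain scores missing after discharge, and the promised comparison of duration of analgesia, which appears in no outcome list. These are valid additions to the fix.

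**Conclusion.** The concern holds. Three lists conflict on the class of delirium and on the pain times, nothing ranks or adjusts the outcomes, and the printed threshold contradicts both power calculations. If any one significant result counts, the false-positive chance for a primary claim is about 16-30% across the readings that test pain times separately, and 12.5-14% with pain as one item of three. These figures rest on the assumed correlations and on that success rule, which the plan neither states nor excludes. The list conflict and the alpha contradiction rest on no assumption. This must be fixed before unblinding, because a primary outcome chosen after the data are seen cannot carry a confirmatory claim.

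**What to change.** 1. Correct the threshold in Statistical Analysis to 0.05 (5%).
2. Reconcile the pain times, the pain scale, the class of delirium and the morphine-equivalent window across Description of Outcome Measures and Study Instruments, and give duration of analgesia a definition and a class.
3. Name one primary outcome, tested once at two-sided 0.05. One summary of the reconciled pain scores, such as each patient's mean, fits the sizing and the stated purpose; say how missing scores are handled. If total morphine equivalents is chosen instead, it needs its own power statement.
4. Test the other key outcomes in a stated fixed sequence. If narcotic use must be claimable even when pain is not significant, use Holm across the pain summary, morphine equivalents and time to ambulation.
5. Name the tests for time to ambulation (for example log-rank, with a rule for patients who never ambulate) and for delirium (for example Fisher's exact test if yes/no).
6. State that the 25-patient update to the IRB makes no efficacy comparison between arms, or give a strict boundary if it does.

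**Cost.** These are wording changes and a summary of data already to be collected, with no extra patients. Single time points and lower-ranked outcomes can no longer each be claimed at 0.05. Averaging pain helps only if the effect persists, and Holm lowers power for pain; step 4 of the working gives both.

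The choice between fixed sequence and Holm matters because "All subjects will have access to rescue analgesics": rescue guided by pain score in both arms may narrow a pain difference, and pain placed first could then block a claim on narcotic use. As an illustration, assume a morphine effect of 0.9 SD (not from the documents), correlation 0.3 and no ambulation effect. The chance of claiming morphine equivalents is:

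| Effect on pain summary | Fixed sequence | Holm |
|---|---|---|
| 0.375 SD | 24% | 76% |
| 0.75 SD | 67% | 78% |
| 0.85-0.95 SD (mean of a constant 1.5/2 effect) | 75-81% | 78-79% |

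Holm is therefore mainly protection against a weak pain effect; with a lasting one the two perform about equally.
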